### 3.2.4 Patient Disposition and Demographics

Demographic, baseline characteristics will be summarized in FAS. Demographic including age, gender, ethnicity, race, region, Familial Partial Lipodystrophy (FPL) Group as entered on the Randomization CRF will be summarized using descriptive statistics. In addition, FPL Group derived based on the data entered on the Disease History CRF and the genetic testing results as below will be summarized.

- Patients with a pathogenic mutation in known FPL genes according to the University of Chicago data (for patients who consented to genetic testing) or historical genetic testing results (for patients who did not consent) will be assigned to Group 1.
  - Patients who do not belong in Group 1 and have a family history of FPL or a similar fat distribution and/or history of fat loss in a first degree relative, plus at least 1 minor criterion as entered in the Disease History CRF will be assigned to Group 2. Minor criteria refers to protocol section 5.1 inclusion criteria.
  - Patients who do not belong in Group 1 or Group 2 and have at least 2 minor criteria as entered in the Disease History CRF and a Screening BMI  $< 35 \text{ kg/m}^2$  will be assigned to Group 3.
  - Patients who do not fall into one of the categories above will be assigned to None.

Baseline characteristics includes: body weight, height at screening, BMI, fasting lipids results including

Baseline data will be listed for all randomized patients.

All screened patients will be included in the summary of patient disposition. The number of patients screened, randomized, dosed, number of patients included in each analysis set, completed treatment, discontinued treatment along with reasons for discontinuing treatment, entered post-treatment follow-up, completed post-treatment follow-up, and discontinued post-treatment follow-up along with reasons for early terminating post-treatment follow-up, will be presented for both randomized treatment period and OLE period by treatment group to which they were randomized, and overall.

Listing of patient disposition will also be provided for all randomized patients.

Medical history will be coded by Medical Dictionary for Regulatory Activities (MedDRA) dictionary Version 19.1 and will be summarized by system organ class and preferred term by treatment and overall for the SAF1 . Medical history will also be provided in the data listings.

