### ***10.6.3 Efficacy Analysis (Primary and Secondary)***

The primary efficacy analysis will be the comparison of percent change from Baseline to the primary analysis time point in fasting TG between ISIS 304801 300 mg once-weekly group and placebo group in the FAS. The data will be analyzed using an analysis of covariance (ANCOVA) model with the randomization stratification factor (diagnosis of disease with or without genetics and family history) and Baseline TG as covariates. In the ANCOVA model, TG will be log-transformed. Patients with a missing primary endpoint will have TG value multiply imputed using an imputation model that contains the following variables: baseline TG, TG values at post-baseline visits and the stratification factor, and the multiple imputation will be stratified by treatment ([Schafer 1997](#); [Schafer 1999](#)). Any patient who discontinues early from the Treatment Period will be strongly encouraged to attend applicable landmark visits including Weeks 12 and 13 during which TG values will be collected and used in the primary analysis.

The primary efficacy analysis will take place after the last patient has completed the Week 52/ET visit and the database has been locked, and will be based on the percent change from Baseline in fasting TG at the primary analysis time point (end of Month 3).

A few sensitivity analyses using controlled imputations (pattern mixture models (PMM) with ANCOVA) will be conducted to assess the robustness of the primary analysis results on both the FAS and PPS. With this approach, missing not at random (MNAR) is assumed and the mean

function for the missing data from patients who discontinue the study is pre-specified in ways that assess the robustness of the MAR assumption. The mean function parameterization will be completed using the following approaches:

- Patients treated with volanesorsen who discontinue the study due to lack of efficacy or Adverse Events or other types of treatment failure will have missing post-treatment discontinuation TG values multiply imputed using estimates from the placebo patients. Specifically, the copy increment from reference (CIR) approaches will be used. Otherwise, non-informative missing data will be imputed using MI method as the same as the primary analysis

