#### For stratification purposes:

Positive on genetic testing: Documentation of pathogenic or likely pathogenic genes associated with familial partial lipodystrophy will be considered positive for genetic analysis if these changes are likely to represent the underlying cause of the subject's phenotype. This should be documented in a written report.

Negative on genetic testing: When sequencing analysis of the partial lipodystrophy panel for variants determines that no pathogenic or likely pathogenic variant were identified or is a variant of unknown significance, this will be considered as evidence for negative for genetics. Negative on genetics will also be considered for those subjects for whom the genetic analysis results are unlikely, unknown, or untested.

Positive family history of FPL or family history of abnormal and similar fat distribution includes immediate family / first degree relatives (father, mother, brother, sister, daughter, son), as well as second degree relatives (grandparents, aunts and uncles, nieces and nephews, and grandchildren).

A permuted block schedule will be used. The Sponsor Quality Assurance department or designee will hold a copy of the randomization lists generated by the IxRS vendor.

Patients who withdraw from the study will not be replaced.

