#### **3.3.2 Analysis of Primary Endpoint**

The primary efficacy analysis will be the comparison of the percent change from Baseline to Randomized Treatment Period Month 3 in fasting triglyceride between volanesorsen group and placebo group in the FAS. The data will be analyzed using an analysis of covariance (ANCOVA) model with the randomization stratification factor (diagnosis of disease with or without genetics and family history) derived based on the Disease History CRF and genetic testing results and treatment group as factors and baseline fasting triglyceride as a covariate. In the ANCOVA model, triglyceride will be log-transformed. Patients with a missing primary endpoint will be excluded from primary efficacy analysis.

The primary efficacy analysis model (ANCOVA) will be repeated for the percent change from baseline in fasting triglyceride at Randomized Treatment Period endpoint month 6 and month 12.

A subgroup analysis of the primary efficacy analysis model (ANCOVA) will also be conducted in the group of genetically confirmed patients according to the University of Chicago data for patients who consented to genetic testing or historical data for patients who did not consent, and for patients with no mutation at month 3, month 6 and month 12. An interaction term of treatment group by derived FPL group will be included as a factor in the ANCOVA model.

The sample SAS code for the ANCOVA model can be found below:

```
*****
* Note: Base = Baseline fasting triglyceride *
*      LOGBASE = Log-transformed baseline fasting triglyceride *
*      PCHG = Percent change from Baseline at Month 3 *
*      TRTP = Treatment group: Placebo, volanesorsen *
*      FPLGRPD = Derived FPL groups: 1 = FPL1, 2 = FPL2, 3=FPL3 *
*      FPL1 - Phenotype + Genetic Variants *
*      FPL2 - Phenotype + No Genetic Variant + Family Hist or Abnormal and *
```

\* Similar Fat + 1 Minor Criterion \*  
\* FPL3 - Phenotype + No Genetic Variant + No Family Hist or Abnormal and \*  
\* Similar Fat + 2 Minor Criteria + BMI<35kg/m2 \*  
\* \*  
\*\*\*\*\*

```
ods output lsmeans=lsm diff=diff;  
proc mixed data = M3TG;  
  class TRTP (ref='Placebo') FPLGRPD;  
  model PCHG = TRTP FPLGRPD LOGBASE /solution cl residual outp=predresid;  
  lsmeans TRTP/e diff cl;  
run;
```

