### **3.3.5 Incomplete or Missing Data**

Patients with a missing primary endpoint will be excluded from primary efficacy analysis.

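### The derived FPL group used in the SAP's ANCOVAs leaves likely pathogenic variants out of Group 1, against SAP 2.2, and can produce a None level that the model key does not list

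*SAP*

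**What the plan says.** **Planned covariate.** Protocol 10.6.3 specifies an "analysis of covariance (ANCOVA) model with the randomization stratification factor" and baseline triglyceride.

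**Covariate to be fitted.** SAP 3.3.2 adjusts for the "randomization stratification factor (diagnosis of disease with or without genetics and family history) derived based on the Disease History CRF and genetic testing results". The sample code fits FPLGRPD, whose key reads "FPLGRPD = Derived FPL groups: 1 = FPL1, 2 = FPL2, 3=FPL3". SAP 3.4.2.1 and 3.4.2.2 use similar models for liver fat and HbA1c, and 3.8 lists the derived factor among the changes to the planned analysis.

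**Genetic rule at stratification.** SAP 2.2, like protocol 4.2, names likely pathogenic and pathogenic as separate variant classes and accepts either: "Documentation of pathogenic or likely pathogenic genes associated with familial partial lipodystrophy will be considered positive for genetic analysis", provided the change is likely to explain the phenotype.

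**Genetic rule in the derivation.** SAP 3.2.4 assigns Group 1 to "Patients with a pathogenic mutation in known FPL genes according to the University of Chicago data", or to patients with a pathogenic mutation in historical results if they did not consent to testing. Groups 2 and 3 follow from family history, minor criteria and BMI. Then: "Patients who do not fall into one of the categories above will be assigned to None".

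**Group as randomized.** In 3.2.4 the FPL "Group as entered on the Randomization CRF will be summarized using descriptive statistics". No model in the SAP uses it.

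**Exclusions.** SAP 3.3.5 gives one: "Patients with a missing primary endpoint will be excluded from primary efficacy analysis".

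**The concern.** Two sections of one SAP define genetically positive differently, and the narrower definition feeds the primary, liver fat and HbA1c models. A programmer would code 3.2.4, because that is where the derivation is written. A patient whom the investigator stratified correctly would then be analysed in a group that he or she was not randomized in, or in a category that the model key does not contain.

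The SAP's Summary of Changes says that the derived group rests on the criteria of Section 2.2. That points to shorthand in 3.2.4 rather than a deliberate narrowing, but the text that governs the derivation does not deliver it.

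At stake are a clear definition of the primary model, some precision, and agreement with the protocol's covariate.

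**Working it through.** **1. Which patients move.** Cross genetics (pathogenic, likely pathogenic, negative) with qualifying family history (yes, no), number of minor criteria (1, 2) and BMI (30, 36): 3 × 2 × 2 × 2 = 24 profiles. A count of zero minor criteria is left out because inclusion 6 requires fatty liver on MRI, which should meet minor criterion e.

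Eligible through the diagnostic routes of protocol 5.1: 16 with a qualifying variant, 4 negative with family history, and 1 negative without family history but with two minor criteria and BMI below 35. The total is 21.

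| Rule | Group 1 | Group 2 | Group 3 | None | Moved from stratum |
|---|---|---|---|---|---|
| 3.2.4 as written | 8 | 8 | 2 | 3 | 8 |
| 3.2.4 aligned with 2.2 | 16 | 4 | 1 | 0 | 0 |

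All 8 that move are likely pathogenic: 4 go to Group 2, 1 to Group 3 and 3 to None. The None profiles have no qualifying family history and either BMI of 35 or more or only one minor criterion. The genetic route in 5.1 requires neither a low BMI nor a minor criterion. If zero minor criteria were allowed (inclusion 6 came in only with Amendment 4), 12 of 29 profiles would move, 7 of them to None.

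**2. The plan's power figure.** With 20 per arm, difference 40, SD 40 and two-sided 0.05, the standard error is 40 × √(1/20 + 1/20) = 12.65. Power is 88.5% (normal) or 86.9% (t), against the stated approximately 80%. About 17 per arm would give 80.7%, so the plan has some slack before this issue arises.

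**3. Cost of a fourth level, by formula.** Assume Group 1 has N = 20, split 10/10, with k of its patients falling in None at random. On average the extra indicator takes up a share [N/(N − 1)]/40 = (20/19)/40 = 0.0263 of the treatment information, whatever k is. The standard error grows by about 1/√(1 − 0.0263) = 1.013.

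**4. Cost of a fourth level, by simulation.** Assumptions: 40 patients, strata 20/10/10, permuted blocks of 4, SD 40, difference 40, and an additive model with treatment, group and one covariate. Between 1 and 4 patients are None. Group effects are nil or 0/20/40 points. There were 6000 runs for standard error and power, and 4000 for type I error.

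- Literal against aligned group: standard error ratio 1.0135 to 1.0153.
- Literal against randomized group, no stratification errors: ratio 1.0135 to 1.0147; power 83% to 85% against 84% to 86%.
- Literal against randomized group, 2 or 4 stratification errors: ratio 0.9956 to 1.0221.
- Randomized against aligned group, 2 or 4 stratification errors: ratio 0.9929 to 1.0190.
- Type I error over all models and scenarios: 0.044 to 0.058 (Monte Carlo standard error 0.0034), consistent with 0.05.

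**5. Estimability.** If all None patients are in one arm, the treatment difference in the additive primary model is still estimable. In the subgroup model with a treatment-by-group interaction, the difference averaged over all four levels is not. Contrasts within Groups 1, 2 and 3 are.

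**The case against.** **In defence of the plan.** The swap is stated in the same sentence of 3.3.2 that keeps the old label, and again in 3.8. The Summary of Changes ties the derived group to Section 2.2, so pathogenic in 3.2.4 may simply be shorthand. A verified diagnostic group is a defensible covariate: 2.2 stratifies untested patients as genetically negative, and protocol Appendix A allows some samples up to Week 12, so the randomized stratum can be wrong. The comparisons above show no consistent precision gain from the randomized stratum over an aligned derived group. All of this stands. It makes the wording of 3.2.4 the core of the point and leaves protocol conformity, not precision, as the reason to prefer the randomized group.

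**Stronger readings that a reader might infer, and that the documents do not support:**

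- *The change was concealed.* It was not. What 3.8 lacks is a reason specific to the covariate, a rule for None and an analysis by randomized group.
- *None patients drop out of the primary analysis.* That would follow only if None were coded as missing. The SAP does not say so, and its one stated exclusion is a missing endpoint, so a fourth level is the natural reading.
- *About 8 in 21 patients are misplaced.* The table counts unweighted profiles, not patients.
- *The subgroup analysis may give no treatment estimate.* With Group 1 split 10/10, the chance that all None patients are in one arm is 2 × C(10,k)/C(20,k) = 47%, 21% or 9% for k = 2, 3 or 4. This affects only the difference averaged over all groups, which the SAP does not name as the reported subgroup result.

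**Conclusion.** The inconsistency between SAP 2.2 and 3.2.4 is real and reaches three efficacy models. The None level and the retained label add avoidable ambiguity. The consequence is small: about 1.4% on the standard error from the extra level and, without stratification errors, about one point of power, with power still above the planned 80%. There is no threat to type I error or to estimability of the primary difference.

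These sizes rest on assumed strata, block size and 1 to 4 None patients. They treat None as a fourth level and do not model likely pathogenic patients who move to Group 2 or 3. The true number affected may be zero. The point merits correction because the primary model should have one consistent definition, not because the result is in danger.

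**What to change.** 1. In SAP 3.2.4, define Group 1 by pathogenic or likely pathogenic variants, as in 2.2. State whether second-degree relatives count for family history: 2.2 includes them, and it is unclear whether the first-degree wording in 3.2.4 is meant to narrow this.
2. In 3.3.2, call FPLGRPD the derived FPL group and list None as a non-missing level, so that no patient in the FAS with an endpoint is dropped. After alignment, None should arise only where CRF or genetic data disagree with eligibility, so list those patients.
3. Run the primary, liver fat and HbA1c ANCOVAs with the FPL group as randomized, taken from the Randomization CRF, and report them beside the aligned derived-group version. Preferably make the randomized version primary, because it is the covariate in protocol 10.6.3.
4. In the subgroup interaction model, report treatment contrasts only within groups that have patients in both arms.

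The cost is SAP wording, one variable name, one key level and one further run of each model. No new data are needed. The drawback is that the randomized stratum keeps any stratification errors. With 2 or 4 of them its standard error is 0.7% smaller to 1.9% larger than that of the aligned group, and the derived-group run covers this.

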### **3.3 Primary Analyses**

Fasting triglyceride and change from baseline (absolute value and percentage of change) will be summarized by analysis visit using descriptive statistics in FAS. Descriptive summary statistics refers to section 3.2.1. Analysis visit includes baseline, endpoint as defined in section 3.2.3, and analysis week as specified in [Appendix B](#).

#### **3.3.1 Primary Endpoint Definition**

The primary endpoint is the percent change in fasting triglyceride from Baseline to the primary analysis time point. The primary analysis time point is at the end of Month 3 where the value is defined as the average of Week 12 (Day 78) and Week 13 (Day 85) fasting assessments.

#### **3.3.2 Analysis of Primary Endpoint**

The primary efficacy analysis will be the comparison of the percent change from Baseline to Randomized Treatment Period Month 3 in fasting triglyceride between volanesorsen group and placebo group in the FAS. The data will be analyzed using an analysis of covariance (ANCOVA) model with the randomization stratification factor (diagnosis of disease with or without genetics and family history) derived based on the Disease History CRF and genetic testing results and treatment group as factors and baseline fasting triglyceride as a covariate. In the ANCOVA model, triglyceride will be log-transformed. Patients with a missing primary endpoint will be excluded from primary efficacy analysis.

The primary efficacy analysis model (ANCOVA) will be repeated for the percent change from baseline in fasting triglyceride at Randomized Treatment Period endpoint month 6 and month 12.

A subgroup analysis of the primary efficacy analysis model (ANCOVA) will also be conducted in the group of genetically confirmed patients according to the University of Chicago data for patients who consented to genetic testing or historical data for patients who did not consent, and for patients with no mutation at month 3, month 6 and month 12. An interaction term of treatment group by derived FPL group will be included as a factor in the ANCOVA model.

The sample SAS code for the ANCOVA model can be found below:

```
*****
* Note: Base = Baseline fasting triglyceride *
*      LOGBASE = Log-transformed baseline fasting triglyceride *
*      PCHG = Percent change from Baseline at Month 3 *
*      TRTP = Treatment group: Placebo, volanesorsen *
*      FPLGRPD = Derived FPL groups: 1 = FPL1, 2 = FPL2, 3=FPL3 *
*      FPL1 - Phenotype + Genetic Variants *
*      FPL2 - Phenotype + No Genetic Variant + Family Hist or Abnormal and *
```

\* Similar Fat + 1 Minor Criterion \*  
\* FPL3 - Phenotype + No Genetic Variant + No Family Hist or Abnormal and \*  
\* Similar Fat + 2 Minor Criteria + BMI<35kg/m2 \*  
\* \*  
\*\*\*\*\*

```
ods output lsmeans=lsm diff=diff;  
proc mixed data = M3TG;  
  class TRTP (ref='Placebo') FPLGRPD;  
  model PCHG = TRTP FPLGRPD LOGBASE /solution cl residual outp=predresid;  
  lsmeans TRTP/e diff cl;  
run;
```

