- Proportion of patients who achieve a  $\geq 40\%$  reduction in fasting TG from Baseline and  $\geq 30\%$  reduction of hepatic fat fraction percent from baseline at Month 6 between ISIS 304801 300 mg once-weekly and placebo group will be analyzed using a logistic regression model with the randomization stratification factors, log transformed Baseline TG, and Baseline hepatic fat fraction as covariates. Missing data will be considered as informative missing for patients who discontinue the study prior to the primary analysis time point due to lack of efficacy or Adverse Events or other types of treatment failure; otherwise, missing data will be considered as non-informative missing. In the responder analysis, patients with informative missing data will be treated as non-responders. Non-informative missing data will be handled using the same multiple imputation method as the primary analysis. Analyses will also be performed in which the above primary and secondary efficacy endpoints are evaluated at the Month 3, Month 6, and Month 12 analysis time points, where applicable. The efficacy endpoints will also be evaluated at Month 15, Month 18, and Month 24 in the OLE period as appropriate.

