### ***3.4.2 Analysis of Secondary Endpoints***

#### ***3.4.2.1 Secondary Endpoint 1: Percent Change from Baseline in hepatic steatosis (as assessed by hepatic fat fraction using magnetic resonance imaging [MRI])***

Hepatic fat fraction (%), change from baseline, and percent change from baseline will be summarized by analysis visit using descriptive statistics in FAS. They will also be summarized separately by genetic mutation category: LMNA+PPARG, or neither. Descriptive summary statistics refers to section 3.2.1. Visit includes baseline and analysis visits according to the visit window defined in [Appendix B](#).

The percent change in Hepatic Fat Fraction (%) from Baseline to month 6 and month 12 at Randomized Treatment Period will be analyzed using the similar ANCOVA model as for the primary efficacy analysis model (ANCOVA).

A subgroup analysis of the ANCOVA will also be run for percent change in hepatic fat fraction in the group of genetically confirmed patients according to the University of Chicago data for patients who consented to genetic testing or historical data for patients who did not consent, and in patients with no mutation at month 6 and month 12 respectively.

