#### ***3.4.2.2 Secondary Endpoint 2: Change from Baseline in HbA1c***

HbA1c (%), change from baseline, and percent change from baseline will be summarized by analysis visit using descriptive statistics in FAS. They will also be summarized separately by genetic mutation category: LMNA, PPARG, or neither. Descriptive summary statistics refers to section 3.2.1. Visit includes baseline and analysis visits according to the visit window defined in [Appendix B](#).

The change in HbA1c from Baseline to Randomized Treatment Period month 3, month 6, month 9 and month 12 will be analyzed using this similar ANCOVA model as for the primary efficacy analysis

A subgroup analysis of the ANCOVA will also be run for change in HbA1c from baseline in the group of genetically confirmed patients according to the University of Chicago data for patients who consented to genetic testing or historical data for patients who did not consent, and in patients with no mutation at month 3, month 6, month 9 and month 12 respectively.

**3.4.2.3 Secondary Endpoint 3: Proportion of patients who achieve a >=40% reduction in fasting triglyceride from Baseline and >=30% reduction of hepatic fat fraction percent from baseline at Month 6**

Frequency and proportion of patients who achieve a >=40% reduction in fasting triglyceride from baseline and >=30% reduction of hepatic fat fraction from baseline at Month 6 will be displayed.

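### Does the unspecific log-transformation sentence leave the primary triglyceride ANCOVA open to two different models?

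*SAP*

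**What the plan says.** SAP 3.3.1 defines the outcome: "The primary endpoint is the percent change in fasting triglyceride from Baseline to the primary analysis time point". SAP 3.3.2 compares that percent change between arms by ANCOVA, with treatment and derived FPL group as factors and baseline fasting triglyceride as covariate. It then adds: "In the ANCOVA model, triglyceride will be log-transformed". Protocol 10.6.3 has the matching sentence, "In the ANCOVA model, TG will be log-transformed", and gives no code.

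The SAP prints code, which it labels as a sample. The response is defined as "PCHG = Percent change from Baseline at Month 3" and the model line is "model PCHG = TRTP FPLGRPD LOGBASE /solution cl residual outp=predresid". LOGBASE is defined there as the log of baseline triglyceride. It is the only logged quantity in the code.

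SAP 3.3.2 repeats the model for percent change at Months 6 and 12. For HbA1c, SAP 3.4.2.2 says the change "will be analyzed using this similar ANCOVA model as for the primary efficacy analysis", and SAP 3.4.2.1 has near-identical wording for hepatic fat fraction. SAP 3.8 withdraws the protocol's sensitivity analyses of the primary result, which included a Wilcoxon test with a Hodges-Lehmann estimate.

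**The concern.** The sentence about logging does not say what is logged. Read alone, it could mean the baseline covariate, the Month 3 value, or both. A statistician who programs log(Month 3/baseline) as the response could claim to follow the text, while one who follows the code models raw percent change. The two answer different questions: a ratio of geometric means, or a difference in mean percent change.

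This is the only primary test. If the scale were open, a verdict near 0.05 could turn on it, and the choice might be made after the results were known. With the rank-based analysis withdrawn, no second test would show whether the answer depends on scale. The same doubt would pass to Months 6 and 12 and, through the word similar, to hepatic fat fraction and HbA1c.

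**Working it through.** **1. Which reading do the documents support?**

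| Place | Baseline logged only | Response logged |
|---|---|---|
| SAP 3.3.2, sentence before the logging sentence: baseline triglyceride is the covariate | fits | silent |
| SAP 3.3.2 code: response PCHG, covariate LOGBASE | fits exactly | contradicts |
| SAP 1.3 hypotheses: equal or different percent change | fits | does not fit |
| SAP 3.3.1 endpoint: percent change | fits | does not fit |
| SAP 3.3.3: SD of 40% for percent change, reductions of 50% and 10% | fits | does not map |
| SAP 3.3.2, Months 6 and 12: percent change | fits | does not fit |
| Log-ratio response or back-transformation for triglyceride | not needed | needed, but absent |

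The expected percent changes are negative (-10 and -50), so the response as defined cannot itself be logged. A log response would need a new variable that neither document defines.

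**2. The plan's own power figure.** Inputs from SAP 3.3.3: 20 per arm, difference 40, SD 40, two-sided 0.05.

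- Standardised difference: 40 / (40 × √(2/20)) = 3.162.
- Normal approximation: Φ(3.162 − 1.960) = 88.5%. Noncentral t: 86.9%.
- The plan states about 80%, so the figure does not reproduce. The gap is on the cautious side and is separate from this point. What matters here is that the inputs are on the raw percent-change scale.

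**3. What each model would estimate.** Assume the Month 3/baseline ratio is log-normal with arithmetic mean m and SD s. Then the log-SD is √ln(1 + (s/m)²) and the geometric mean is m / √(1 + (s/m)²).

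- Placebo, m = 0.90, s = 0.40: log-SD 0.42, geometric mean 0.9/√1.1975 = 0.822.
- Active, m = 0.50, s = 0.40: log-SD 0.70, geometric mean 0.5/√1.64 = 0.390.
- Raw difference: −40 points. Ratio of geometric means: 0.390/0.822 = 0.475, or about 52% lower.

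The shift from 40 to 52 is a change of estimand, not a bias. If both arms had the same log-SD, the ratio would be 0.50/0.90 = 0.556, or 44.4% lower. So part of the contrast comes from the unequal log-SDs that equal raw SDs imply.

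**4. Disagreement if a log response were meant.** 20,000 simulated trials per setting, with true mean changes of −10% (placebo) and −50% (active). Both models adjust for treatment, stratum and log baseline. Assumed: log-baseline SD 0.7 with no slope, and strata 50/25/25 with no effect.

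| SD placebo/active | Per arm | Power, code | Power, log ratio | Verdicts differ |
|---|---|---|---|---|
| 40/40 | 20 | 83% | 96% | 13% |
| 40/30 | 20 | 92% | 97% | 5% |
| 40/20 | 20 | 98% | 99% | 1% |
| 40/14.1 | 20 | 99.4% | 99.2% | 0.5% |
| 70/20 | 20 | 72% | 62% | 16% |
| 40/40 | 15 | 73% | 89% | 16% |

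The SD of 14.1 is the largest of the three Phase 2 active-arm values for triglyceride in Protocol Table 1 (8.3, 14.1 and 8.9). A second set of 8,000 trials per setting, with a different assumed baseline distribution and stratum mix, gave 13.0% at 40/40. It gave 4.0% with a common log-SD of 0.5 and 14.9% with a common log-SD of 0.7.

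**5. Under the null** (−10% in both arms), each model rejected in 5.0% of trials in the first set and 4.8% in the second. In the second set the log model alone rejected in 1.3%, so at least one rejected in 4.8% + 1.3% = 6.1%. That bounds the inflation from picking freely between the two after the fact.

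**The case for a change.** The strongest case for acting has four parts. First, elsewhere the protocol names the logged term in full, "log transformed Baseline TG, and Baseline hepatic fat fraction as covariates", so its absence here could be deliberate. Second, the code is only a sample, and no rule ranks it above the text. Third, SAP 3.8 describes the triglyceride analysis as one of change from baseline, a further wording. Fourth, with the rank-based test gone, no formal check on scale remains.

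Some of this stands. The sentence is incomplete, and the formal scale check has been withdrawn, openly. The rest is weaker than it looks:

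- The contrasting phrase belongs to a logistic model with a binary response, where baseline is the only triglyceride term that could be logged. If anything, it shows that logging baseline triglyceride as a covariate was the sponsor's practice.
- The model is printed, and SAP section 1 requires any departure from the final plan to be justified and documented in the study report. A switch to a log response would depart visibly from both the code and the stated endpoint, so the choice is less open than feared.
- SAP 3.2.1 and 3.3 plan medians, quartiles and ranges of absolute and percent change by visit, and the code outputs residuals. These are not tests, but they would show marked skew.
- For hepatic fat fraction and HbA1c, the logging sentence speaks only of triglyceride. Protocol 10.6.3 gives both models plain baseline and stratum as covariates.

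A log-ratio primary model is a reasonable design choice in its own right, but not a correction. It replaces the stated estimand, separates the model from the planning SD, and in one setting above has less power (62% against 72%).

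**Conclusion.** No change follows. The wording is loose, but every specific statement about the primary analysis points the same way: the response is raw percent change and only the baseline covariate is logged. On that reading text and code agree, the effect on the result is zero, and the printed model gives a test at about 5% in the null simulations on the endpoint the plan defines. Adding the word baseline would tidy the sentence without altering any result. Restoring a rank-based analysis would add information but correct no error.

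The 0.5% to 16% disagreement applies only if a log response was intended, which is the less supported reading. It also rests on a log-normal ratio and on SDs chosen for illustration. The 13% figure needs a raw SD of 40 points in both arms, and so an active log-SD of 0.70 against 0.42 on placebo. The Phase 2 SDs come from other patient populations and may understate the spread in FPL, but they are the only observed triglyceride SDs in the documents, and at the largest of them the disagreement is 0.5%.
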